5.7 Statistical models

5.7.1 Primary analysis

The primary analysis of PCR-corrected ACPR at Day 29 is detailed in [Section 2](#).

SAS procedure FREQ with EXACT statement for one-way tables will be used to estimate the proportion of responders (binary outcome = 1 or “Yes”), along with the associated 95% (=100 × (1 – two-sided *alpha level*)) two-sided Clopper- Pearson CI.

1. For exploratory purpose, 2-sided 95% confidence intervals for the difference in ACPR at Day 29 between two KAF156/LUM-SDF treatment groups with optimal dose will be constructed for Cohorts 2 and 3 using the Wilson uncorrected method.

Wilson uncorrected method:

Let

a = # responders in the fed arm

c = # non-responders in fed arm

m = sample size of the fed arm (a+c)

b = # responder in the fasted arm

d = # non-responders in the fasted arm

n = sample size of the fasted arm (b+d)

$\theta = \pi_1 - \pi_2$ is the difference between two arms

$\hat{\theta} = \frac{a}{m} - \frac{b}{n}$ is estimated difference between two arms

Method based on the Wilson score method for the single proportion, without continuity correction:

$L = \hat{\theta} - \delta$, $U = \hat{\theta} + \varepsilon$ where

$$\delta = \sqrt{\{(a/m - l_1)^2 + (u_2 - b/n)^2\}} = z\sqrt{\{l_1(1 - l_1)/m + u_2(1 - u_2)/n\}}$$

$$\varepsilon = \sqrt{\{(u_1 - a/m)^2 + (b/n - l_2)^2\}} = z\sqrt{\{u_1(1 - u_1)/m + l_2(1 - l_2)/n\}}$$

l_1 and u_1 are the roots of $|\pi_1 - a/m| = z\sqrt{\{\pi_1(1 - \pi_1)/m\}}$, and l_2 and u_2 are the roots of $|\pi_2 - b/n| = z\sqrt{\{\pi_2(1 - \pi_2)/n\}}$.

Where z is the standard normal deviate associated with 5% level of significance (l.o.s.) two sided.

5.7.2 Key secondary analysis

NA

5.7.3 Other secondary/exploratory analysis

Kaplan-Meier estimates

An estimate of the survival function in each treatment group will be constructed using Kaplan-Meier (product-limit) method as implemented in PROC LIFETEST with METHOD=KM option. The PROC LIFETEST statement will use the option CONFTYPE=LOGLOG.

Median survival for each treatment group will be obtained along with 95% confidence intervals calculated from PROC LIFETEST output using the method of [Brookmeyer and Crowley 1982](#). Kaplan-Meier estimates of the survivor function with 95% confidence intervals at specific time points will be summarized. The standard error of the Kaplan-Meier estimate will be calculated using Greenwood's formula [Collett 1994](#).

Difference in responder rates stratified by cohort using Mantel-Hanszel estimate

For PCR corrected and uncorrected ACPR rates, the between treatment difference will be evaluated using a Mantel-Haenszel estimate of the treatment difference in responder rates stratified by cohort using PROC FREQ with RISKDIFF(COMMON) option in the TABLES statement).

Difference in responder rates using the Wilson uncorrected method

For PCR corrected and uncorrected ACPR rates, the between treatment difference will be evaluated using a Wilson uncorrected method using PROC FREQ with RISKDIFF (CL=NEWCOMBE) option in the TABLES statement.

Difference in parasite clearance (fever clearance) rate using log-rank test

For parasite clearance and fever clearance rates, the between treatment difference will be evaluated using log-rank test using PROC LIFETEST with STRATA <treatment> and TEST <treatment> statements. For pooled time to event data from cohort 1 and 2, stratified log-rank test will be performed using GROUP = <cohort> option in STRATA statement.

Confidence interval for Post treatment max QTcF/QTcB increase from baseline

For maximum increase in QTcF/QTcB from baseline, 2-sided $100 \times (1 - \alpha) \%$ confidence intervals (CI) for the difference between the 2 treatment groups will be calculated using PROC TTEST by assuming normality of data.

Confidence interval for geometric mean ratio

For PK parameters, such as AUC_{0-24h} , C_{max} , the values for individuals will be converted into \log_e scale. Mean difference and corresponding 2-sided $100 \times (1 - \alpha) \%$ confidence intervals (CI) will be calculated using PROC TTEST by assuming normality of data on log scale. The geometric mean, the lower and upper confidence limits will be calculated by exponentiating the difference, and lower and upper confidence limit that were derived using log data.

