#### Cohorts 1 and 2:

Approximately 220 (up to 268 in case Cohort 2 stops early and additional patients are enrolled in Cohort 1) male and female pediatric patients (6 months to < 12 years old) will be randomized to the study. There will be two sequential age-descending cohorts of approximately 140 patients for Cohort 1 and 80 patients for Cohort 2: Cohort 1 will include children 2 to < 12 years and Cohort 2 will include children 6 months to < 2 years (Figure 3-1 and Figure 3-2). In the event that Cohort 2 is stopped early, such as after the first 24 patients, 80 additional patients will be enrolled in Cohort 1. Randomization will be stratified by age group (6 years to < 12 and 2 to < 6 years) and country for Cohort 1, and by country for Cohort 2. Children will have a body weight  $\geq 10$  kg in Cohort 1 and  $\geq 5$  kg in Cohort 2.

The Screening Period for the three cohorts will consist of two visits: a Pre-Screening visit and a Screening visit.

- **Pre-Screening visit:** Pre-screening is a key element to successfully identify the right patients to be screened for this clinical study. During pre-screening, a *P. falciparum* parasite count will be obtained. Patients in the Run-in cohort should have a *P. falciparum* parasitemia of  $\geq 1,000$  and  $\leq 150,000$  parasites/ $\mu$ L at the time of the pre-screening visit to be further screened. Patients Cohort 1 and Cohort 2 should have a *P. falciparum* parasitemia of  $\geq 1,500$  and  $\leq 150,000$  parasites/ $\mu$ L at the time of the pre-screening visit to be further screened.
- **Screening visit:** Further screening assessments will take place as soon as the pre-screening *P. falciparum* parasitemia outcome is available and only if outcome is in the pre-defined range ( $\geq 1,000$  and  $\leq 150,000$  parasites/ $\mu$ L in Run-In Cohort and  $\geq 1,500$  and  $\leq 150,000$  parasites/ $\mu$ L in Cohort 1 and Cohort 2 ).

It is not permissible to re-screen a patient within the same malaria episode if s/he fails the initial pre-screening or screening. Re-screening of a patient may occur in case the patient is returning to the study site for a new malaria episode. In this case, the patient will be assigned a new study number.

All eligible patients will be admitted to the hospital on Day 1. Another *P. falciparum* parasite count will be obtained prior to dosing on Day 1. The outcome of the Day 1 visit parasite count will be used as the baseline count.

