### 6.1.3 Treatment arms/group

Patients will be assigned to one of the 2 treatment groups in a ratio of 1:1 per cohort as follows:

- The starting dose of KAF156 and LUM-SDF for the Run-in Cohort (12 to < 18 years) will be as per Table 6-2. After the Run-in Cohort, a dose and food recommendation will be selected for children < 12 years old.
- Children in Cohorts 1 and 2 (Cohort 1: 2 to < 12 years; Cohort 2: 6 months to < 2 years) who are randomized to KAF156 and LUM-SDF combination will take a proportion of the selected dose per weight group as in Table 6-3.
- Children in Cohorts 1 and 2 (Cohort 1: 2 to < 12 years; Cohort 2: 6 months to < 2 years) who are randomized to Coartem® will take a proportion of the selected dose per weight group as in Table 6-4.

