### **PCT and FCT:**

Descriptive statistics (mean, standard error, median, quartiles) will be presented using the Kaplan-Meier method. Kaplan-Meier curves will be provided.

PCT will be calculated based on uncorrected parasite counts. Patients without parasite clearance for whatever reason will be censored at the time of last parasite assessment. Patients who were enrolled on the basis of history of fever and did not subsequently have a fever at pre-dose will not be included in the analysis of FCT. Patients without fever clearance for whatever reason will be censored at the time of last temperature assessment.

For Cohorts 1 and 2 pooled, the treatment difference between KAF156 and LUM-SDF and Coartem® will be evaluated at the 2-sided 5% significance level using a log-rank test stratified by cohort. For each cohort, the treatment difference between 2 treatment groups will be evaluated at the 2-sided 5% significance level using a log-rank test.

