All post-text tables will be generated using Microsoft Word cell-based format so that they can be easily cut and pasted to create intext tables for the CSR. For the run-in cohort, some treatment groups may consist of doses that are not optimal. All such treatment groups will also be displayed in the post-text tables along with the ones that are the optimal. However, only those treatment groups containing the optimal dose for the run-in cohort are important for displaying in the intext tables. Therefore, post-text tables will display all cohorts including the pooled cohort (if applicable) and all treatment groups under a cohort side by side as columns. Within each cohort, the 2 treatment groups will be displayed side by side.

Although randomization is stratified using country and age category per [Table 1-1](#) statistical analysis will not be stratified accordingly due to small sample sizes in each country/age category. For pooled analyses, study cohort will be used as stratum.

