2.7.2.4 Parasite clearance time (PCT) and fever clearance time (FCT)

Descriptive statistics (mean, standard error, median, quartiles) will be presented using the Kaplan-Meier method. Kaplan-Meier curves will be provided.

PCT will be calculated based on uncorrected asexual parasite counts. Patients without parasite clearance for whatever reason will be censored at the time of last parasite assessment. Patients who were enrolled on the basis of history of fever and did not subsequently have a fever at pre-dose will not be included in the analysis of FCT. Patients without fever clearance for whatever reason will be censored at the time of last temperature assessment. Patients who received any antimalarial medication (including rescue medication) before (parasite or fever) clearance will be censored at the first use of antimalarial medication. If the study medication is vomited in the same date as the use of antimalarial medication, the last vomiting time on the study medication date is imputed as time of antimalarial medication. Otherwise, the antimalarial medication time can be imputed using the middle day time (12:00). The between treatment difference will be evaluated exploratorily using a log-rank test separately by cohort and stratified by cohort for pooling Cohorts 1 and 2 if cohort 2 does not stop early; otherwise log-rank test will be performed for Cohorts 1 and 2 separately.

Additional analysis for FCT will be performed by excluding patients who took anti-pyretic drugs (ATC2 code as N02 or M01) prior to FCT.

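### SAP 5.7.3 swaps the roles of treatment and cohort in the code for the pooled PCT and FCT log-rank test, so coded literally it compares Cohort 1 with Cohort 2

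*SAP*

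**What the plan says.** The intended test is stated consistently in three places:

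- Protocol 12.5.1 (PCT and FCT): for Cohorts 1 and 2 pooled, the difference between KAF156/LUM-SDF and Coartem "will be evaluated at the 2-sided 5% significance level using a log-rank test stratified by cohort".
- SAP 2.7.2.4: the between-treatment difference is assessed by a "log-rank test separately by cohort and stratified by cohort for pooling Cohorts 1 and 2 if cohort 2 does not stop early".
- SAP 2.1, as a general rule: "For pooled analyses, study cohort will be used as stratum".

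SAP 5.7.3 turns this into SAS terms. It opens with the same aim: "For parasite clearance and fever clearance rates, the between treatment difference will be evaluated using log-rank test". It then specifies the test "using PROC LIFETEST with STRATA <treatment> and TEST <treatment> statements". For pooled data from Cohorts 1 and 2 it adds that a "stratified log-rank test will be performed using GROUP = <cohort> option in STRATA statement".

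SAP 2.7.2.4 calls the comparison exploratory. SAP 2.7.2 says that the secondary endpoints carry no pre-specified hypotheses and are supportive.

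**The concern.** The code and the text give cohort opposite roles. SAP 2.1 makes cohort the stratum, but SAP 5.7.3 leaves treatment in the STRATA position and attaches cohort to GROUP=. In PROC LIFETEST, once GROUP= is given, its variable names the groups compared and the STRATA variables are what the test is stratified on. A programmer who copies the specification gets Cohort 1 against Cohort 2, stratified by treatment.

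Such a program would run without complaint and return a plausible p-value. That p-value would be labelled as a treatment comparison of PCT or FCT, yet it would respond to differences between children aged 6 months to under 2 years and those aged 2 to under 12 years, and not to treatment. SAP Section 4 declares no change from the protocol-specified analyses, so it would also be an undeclared departure from Protocol 12.5.1.

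**Working it through.** **1. Roles of the variables in the pooled test**

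| Source | Compared | Stratum |
|---|---|---|
| Protocol 12.5.1 | treatment | cohort |
| SAP 2.1 (pooled analyses) | not specified | cohort |
| SAP 2.7.2.4 | treatment | cohort |
| SAP 5.7.3, code as written | cohort (GROUP=) | treatment (STRATA) |

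The pooled sentence does not repeat the STRATA variable, but no reading with cohort in GROUP= compares treatments. The meaning of GROUP= is general knowledge of the software and is not stated in either document. The conflict over which variable is the stratum is visible in the text.

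**2. Does the TEST statement rescue it?** No. TEST statistics are pooled over the STRATA levels. With treatment in both statements, treatment is constant within each stratum, so its within-stratum variance is 0 and there is nothing to test.

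**3. Size.** The documents give no power or sample size for this test, so there is no planned figure to reproduce.

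Inputs from the documents: cohort sizes of "approximately 140 patients for Cohort 1 and 80 patients for Cohort 2" (Protocol Section 3); "Patients will be assigned to one of the 2 treatment groups in a ratio of 1:1 per cohort" (Protocol 6.1.3), hence 70+70 and 40+40; two-sided 5% (Protocol 12.5.1).

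Assumptions not in the documents: hazard ratio (HR) 1 or 1.5; exponential times with a 24 h mean; censoring at 168 h. Under these, 1 − exp(−168/24) = 1 − exp(−7) = 0.999, so nearly all 220 children have an event.

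Schoenfeld approximation: power = Φ(√(D·p·(1−p)) · |ln HR| − 1.96), with D = 220 and ln 1.5 = 0.405.

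- Treatment HR 1.5, intended test, p = 0.5: √(220 × 0.25) = 7.42; 7.42 × 0.405 − 1.96 = 1.05; power 85.2%.
- Cohort HR 1.5, test as coded, p = 140/220 = 0.636: √(220 × 0.636 × 0.364) = 7.14; 7.14 × 0.405 − 1.96 = 0.93; power 82.5%.

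Simulated rejection rates, 2,000 trials per scenario:

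| True effects | Intended (treatment, stratified by cohort) | As coded (cohort, stratified by treatment) |
|---|---|---|
| none | 5.0% | 5.8% |
| treatment HR 1.5 only | 84.7% | 5.6% |
| cohort HR 1.5 only | 5.1% | 80.9% |
| both HR 1.5 | 82.8% | 80.6% |

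The two methods agree. The coded test stays near 5% whatever the treatment effect, and it tracks the cohort effect.

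**4. Where these figures do not apply.** They need about 220 events. FCT has fewer, because children without fever at pre-dose are excluded (Protocol 12.5.1, SAP 2.7.2.4). For recrudescence, the 95% response assumed in Protocol 12.8.1 implies roughly 0.05 × 220 = 11 events. With D = 11, even the correct test has only about 10% power at a treatment HR of 1.5 (√(11 × 0.25) = 1.66; 1.66 × 0.405 − 1.96 = −1.29).

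**The case against.** The strongest reply is that the governing text is already right. Protocol 12.5.1, SAP 2.1 and SAP 2.7.2.4 all describe the correct test, and SAP 5.7.3 itself opens by naming the between-treatment difference. A programmer working from SAP 2.7.2.4 would run the right analysis. SAP 5.7.1 still describes fed and fasted arms and a Cohort 3, so this appendix plainly carries stale text and is a weak guide to what will be run. The comparison is also exploratory and supportive, and the pooled test is dropped if Cohort 2 stops early.

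All of this stands, and it limits the consequence. A reader might infer that the trial will report an age comparison as a treatment comparison. The documents do not support that; they show only that this would happen if the code were followed literally.

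A reader might also infer that the pooled recrudescence and new-infection tests are wrong by the same code. The log-rank paragraph of SAP 5.7.3 is headed and introduced for parasite and fever clearance only, and SAP 2.7.2.5 and 2.7.2.6 cite no code. Those tests are affected only if the code is reused.

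The reply does not remove the error. Section 5.7 is where the SAP gives its SAS implementation, this is its only log-rank code, and it contradicts the SAP's own rule for pooled analyses.

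**Conclusion.** The pooled log-rank specification in SAP 5.7.3 is wrong as written and should be corrected. If coded literally, the pooled exploratory PCT and FCT p-values would not respond to treatment and would respond to age cohort. For PCT, with about 220 events and illustrative hazard ratios of 1.5, a cohort effect alone is flagged in about 80–83% of trials. A treatment effect alone is flagged in about 5%, against about 85% with the intended test. Neither the hazard ratios nor the event count comes from the documents, and the figures should not be carried over to FCT, recrudescence or new infection.

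The problem arises only if Cohort 2 does not stop early. The by-cohort test, with treatment in STRATA and no GROUP= option, is valid as written; there the TEST statement is merely superfluous. It would be a mistake to infer any threat to the primary conclusion: the Mantel-Haenszel non-inferiority analysis uses a different procedure and is not touched.

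**What to change.** In SAP 5.7.3:

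- Pooled Cohorts 1 and 2: `STRATA cohort / GROUP=treatment TEST=LOGRANK`.
- Within a cohort: keep treatment as the STRATA variable, without GROUP=.
- Delete the TEST statement for treatment.
- If the code is reused for the pooled recrudescence and new-infection tests (SAP 2.7.2.5 and 2.7.2.6), use the corrected form and say so.

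The cost is one line of SAP text and the matching line of code. No planned analysis changes; the code is brought into line with Protocol 12.5.1, SAP 2.1 and SAP 2.7.2.4. If the programs are already written, check the STRATA statement and rerun the pooled p-values where needed.

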## **12-lead ECG:**

PR, QRS, QT, QTcF, QTcB, and RR intervals will be obtained from 12-lead ECGs for each patient during the study. ECG data will be read and interpreted (centrally).

Categorical Analysis of QT/QTc interval data based on the number of patients meeting or exceeding predefined limits in terms of absolute QT/QTc intervals or changes from baseline will be presented. In addition, a listing of these patients will be produced (by cohort and treatment group). Post treatment max QTc increase from baseline will be calculated for each patient and 2-sided confidence intervals for the difference between the 2 treatment groups will be calculated using the 80% confidence level for Run-in Cohort and the first 24 patients in Cohort 2 for Data Review checks and the 90% confidence level for all patients in each cohort at the final analysis.

All ECG data will be listed by cohort, treatment group, patient and visit/time, abnormalities will be flagged. Summary statistics will be provided by cohort, treatment group, and visit/time.

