2.8.3 Other safety data

2.8.3.1 ECG and cardiac imaging data

Average triplicate ECG measurements will be used for the summary.

The following quantitative variables will be summarized: heart rate, RR interval, PR interval, QRS interval, QT interval, QTcF (QT interval corrected for heart rate according to Fredericia) and QTcB (QT interval corrected for heart rate according to Bazett) for each timepoint and maximum post baseline value.

Descriptive summary statistics for the change from baseline for each post-baseline visit will be performed by ECG parameters and treatment group.

To assess the dynamics of QTc, HR and body temperature, patients with notable QT, HR and fever (≥ 37.5 °C, axillary equivalent) by timepoint will be provided. Notable criteria is provided below.

To assess the temporal correlations, mean change of QTcF over time, mean change of ECG HR over time, mean change of temperature over time, and PK concentration of KAF156 and lumefantrine over time will be plotted with all panels aligned on the x-axis (Time after dosing).

Post treatment max QTcF/QTcB increase from baseline will be calculated for each patient and 2-sided confidence intervals for the difference between the 2 treatment groups will be calculated based on two sample t-test using the 80% confidence level for the run-in cohort.

Post treatment QTcF/QTcB increase from baseline at common post-baseline timepoints (48H, Day 8, and Day 43) will be calculated for each patient and 2-sided confidence intervals for the difference between the 2 treatment groups will be calculated based on two sample t-test using the 90% confidence level for Cohorts 1 and 2.

QTc will be summarized categorically by computing the number and percentage of patients at each time point and at the maximum post baseline value with following:

- QT, QTcF, or QTcB
 - > 450 and \leq 480 ms
 - > 480 and \leq 500 ms
 - > 500 ms
 - Increase from Baseline of \geq 30 ms to < 60ms
 - Increase from Baseline of \geq 60 ms
- HR for age <18 years
 - > 90th percentile defined in [Table 2-2](#)
 - < 10th percentile defined in [Table 2-2](#)
- PR
 - Increase from baseline >25% and to a value > 200 ms
 - New value of > 200 ms
- QRS
 - Increase from baseline >25% and to a value > 120 ms
 - > 120 ms

Table 2-2 Heart rate cut-offs (beats/minute) based on centile charts

Age Range#	10 th percentile	90 th percentile
Birth	107	148
0 – <3m	123	164
3 – <6m	120	159
6 – <9m	114	152
9 – <12m	109	145
12 – <18m	103	140
18 – <24m	98	135

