Mean and median max QTcF changes from baseline were similar between the POC study KAF156X2201 with KAF156 alone and KAF156A2202 Part 'A' with LUM-SDF (internal data), which indicated that lumefantrine may not contribute to additional QTcF changes when in combination with KAF156. Therefore, we hypothesized that increase in lumefantrine exposure under fed condition may not further increase QTcF. The purpose of QTcF checking for the first 24 patients in the Run-in cohort is to ensure that there is no unacceptable increase in QTcF with food intake. A QTc increase of > 20 ms for a drug compared to placebo is listed as a serious concern in ICH E14 (2005). Hence, a NI margin of 20 ms is selected for comparing the 2 treatment groups in QTcF changes for the first 24 patients in the cohort. Considering that about 15% patients may not be evaluable for QTc change, about 10 patients per treatment group will be considered for the power calculation. In CKAF156A2202 study, the SD for maximum change from baseline to any post baseline was about 20 ms in the 8 arms. Assuming a SD of 20 ms and there is no difference in QTcF change between the 2 treatment groups, there is an 80% power to show that the treatment group with fed does not increase QTcF more than 20 ms compared to the treatment group under fasting using 2-sided 80% confidence interval (i.e., the upper limit of 2-sided 80% confidence limit for the difference between two treatment groups (fed Vs fasted) in mean maximum QTcF change is less than 20 ms) (nQuery Advisor 7.0 module MTE0-1).

4 Change to protocol specified analyses

None

5 Appendix

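### The QTcF/QTcB group comparisons use an unadjusted t-test on change from baseline; adding an ANCOVA on the baseline value already collected would be a cheap gain in precision

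*SAP*

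**What the plan says.** SAP 2.8.3.1 sets two comparisons of QTc change between treatment groups.

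- **Run-in Cohort (fed against fasted):** each patient's maximum post-treatment QTcF/QTcB increase, with the interval "calculated based on two sample t-test using the 80% confidence level for the run-in cohort".
- **Cohorts 1 and 2 (KAF156/LUM-SDF against Coartem):** change at 48 hours, Day 8 and Day 43, also by two-sample t-test, at the 90% level.

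SAP 5.7.3 gives the implementation for the maximum increase: the interval for "the difference between the 2 treatment groups will be calculated using PROC TTEST by assuming normality of data". Protocol 12.5.2 (12-lead ECG) defines the same variable: "Post treatment max QTc increase from baseline will be calculated for each patient".

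SAP 3.1.2 and Protocol 12.8.2 size the run-in check in the first 24 patients. On the margin: "Hence, a NI margin of 20 ms is selected for comparing the 2 treatment groups in QTcF changes". On the assumptions: "Assuming a SD of 20 ms and there is no difference in QTcF change between the 2 treatment groups". The claim is that "there is an 80% power to show that the treatment group with fed does not increase QTcF more than 20 ms", judged on the upper limit of a two-sided 80% interval with about 10 evaluable patients per group.

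The baseline value is available. SAP 2.1.1 defines it as the last pre-dose measurement, Protocol Table 8-1 schedules a screening ECG, and SAP 2.8.3.1 averages the triplicates. Neither document plans a baseline-adjusted QTc model, and SAP 2.1 says the analysis will not use the randomization strata.

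**The concern.** A change score subtracts baseline but does not remove its influence. Change is usually negatively correlated with baseline, because a patient whose baseline reading happens to be high tends to show a smaller rise. The maximum of several post-dose readings is taken against one shared baseline, so error or a transient deviation in that baseline enters the outcome directly. The baseline here is taken during acute malaria, and Protocol 10.2.4 notes that QTc and heart rate move with the illness and recovery.

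With about 10 patients per group, the groups can differ in mean baseline QTcF by chance. If change depends on baseline, part of that difference passes into the fed-minus-fasted estimate. What is at stake is precision in a small safety comparison with a 20 ms margin, when a value already in the database could reduce the noise.

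**Working it through.** **Inputs from SAP 3.1.2 (same in Protocol 12.8.2).** n = 10 per group; SD of maximum change 20 ms; margin 20 ms; true difference 0; two-sided 80% interval, so one-sided alpha 0.10. The 20 ms is already the SD of the change score. The 10 per group follows from 24 x 0.85 / 2 = 10.2.

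**Step 1: the plan's own figure.** SE = 20 x sqrt(2/10) = 8.94 ms. Non-centrality = 20 / 8.94 = 2.236. With 18 df the one-sided 10% critical value is 1.330. Power from the non-central t distribution is 81.7%. The stated 80% is reproduced.

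**Step 2: effect of chance imbalance on the t-test estimate.** Let r be the correlation of change with baseline. The standard error of the difference in baseline means is sqrt(2/10) = 0.447 baseline SDs. The slope of change on baseline is r x 20 ms per baseline SD. A one-standard-error imbalance therefore shifts the estimate by 20 x |r| x 0.447 = 8.94 x |r| ms. No assumption about the size of the baseline SD is needed.

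**Step 3: power with ANCOVA.** Regress change on treatment group and baseline. Residual SD = 20 x sqrt(1 - r²), with 17 df. Estimating the slope inflates the variance by about 1 + 1/(N - 4) = 1 + 1/16 = 1.0625, with N = 20. Power again comes from the non-central t, with SE = residual SD x sqrt(0.2 x 1.0625). For |r| = 0.5: residual SD 17.32, SE 7.98, non-centrality 2.505, critical value 1.333, power 87.7%.

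| Assumed abs(r) | Shift per 1-SE imbalance (ms) | t-test power | ANCOVA power |
|---|---|---|---|
| 0 | 0 | 81.7% | 79.8% |
| 0.2 | 1.8 | 81.7% | 81.0% |
| 0.3 | 2.7 | 81.7% | 82.5% |
| 0.4 | 3.6 | 81.7% | 84.8% |
| 0.5 | 4.5 | 81.7% | 87.7% |
| 0.6 | 5.4 | 81.7% | 91.4% |
| 0.7 | 6.3 | 81.7% | 95.4% |

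Break-even is at |r| of about 0.25. A gain of 5 points needs about 0.47. At r = 0 the loss is 81.7 - 79.8 = 1.9 points.

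**Step 4: simulation.** With 40,000 replicates per scenario, these powers were matched to within about half a point. Both methods were unbiased on average. When the true difference was 20 ms, both passed in about 10% of trials, as they should.

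**Step 5: what r might be.** The documents do not give it. If baseline and maximum post-dose QTcF had equal SD s (an assumption), a change SD of 20 ms implies |r| = 10/s. That is 0.67, 0.50, 0.40 and 0.33 for s = 15, 20, 25 and 30 ms, and it falls below break-even only if s exceeds 40 ms. A wider post-dose spread lowers it. With baseline SD 20 and post-dose SD 24, the baseline-to-post-dose correlation is (400 + 576 - 400)/(2 x 20 x 24) = 0.6, and r = (0.6 x 480 - 400)/400 = -0.28. A gain is plausible but not certain.

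**The case against.** The strongest reply is that nothing in the plan falls short. The check was sized for this t-test using the SD of the change score, and its stated power reproduces. A reader might infer that the plan loses power. It does not: power is forgone only relative to another valid method, and only if |r| exceeds about 0.25. That reply stands.

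A reader might also infer that the estimate is biased. Randomization rules that out. The t interval already allows for chance imbalance and keeps its error rate, and the effects of acute illness act on both groups alike. What remains is conditional: given an observed imbalance, the unadjusted estimate is off in a predictable direction that adjustment would remove. The QTcF limit of 450 ms at screening (Protocol 5.2) and the averaging of triplicates may also narrow the baseline spread or reduce regression to the mean, which is a reason not to assume a large |r|.

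A third tempting reading is that this interval decides whether food is acceptable. The documents do not say so. Protocol 6.7.2 ties a change in the food recommendation to observed lumefantrine Cmax, and Protocol Section 3 describes an integrated review of safety, efficacy and exposure. The QTcF check is one safety input among several, alongside categorical QTc summaries and individual alert rules.

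Nor does the run-in argument carry over whole to Cohorts 1 and 2. There the variable is change at fixed times, no margin is set, and the planned cohorts are about 140 and 80 patients.

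Timing also counts. The latest SAP entry, dated 24-06-2024, follows a dry run for the study report, and Protocol 6.4 left run-in treatment open to the trial team. Replacing the run-in analysis now would be a post-hoc change. This is why the t-test should stay.

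**Conclusion.** The point holds as a cheap improvement. The planned t-test is valid and meets its stated power (81.7% against 80%), but it leaves a usable baseline measurement out of a small comparison. For the run-in check at 10 per group, ANCOVA would change power from 81.7% to between 82.5% and 95.4% for |r| from 0.3 to 0.7, and would remove a shift of 8.94 x |r| ms per one-standard-error imbalance. Below |r| of about 0.25 it would cost up to 1.9 points.

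All of this rests on the plan's SD of 20 ms, a linear relation between change and baseline, and an r that the documents do not report. For Cohorts 1 and 2 the benefit is precision only. No conclusion follows about the correctness of any food recommendation.

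**What to change.** In SAP 2.8.3.1 and 5.7.3, add an analysis of covariance of QTcF (and QTcB) change on treatment group and the baseline value. Report the adjusted difference at the levels SAP 2.8.3.1 already sets: 80% for the Run-in Cohort and 90% for Cohorts 1 and 2. Keep the t-test result beside it. Where run-in data are already known by group, label the run-in ANCOVA as supportive.

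The cost is one model statement and one degree of freedom, with no new data. The only downside is the small loss of power if baseline and change prove nearly uncorrelated.
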